9.1.1 Baseline Values

Data and Measures collected at Visit 1, before any study treatment administration, are considered as baseline values.

9.1.2 Duration of Exposure

The planned treatment duration was of 8 weeks.

9.1.3 Treatment Compliance

The Investigator was responsible for ensuring the accountability of the study product.

The Investigator should maintain records that adequately documented:

- that the subjects were provided with the quantities specified by the clinical investigation plan/amendment(s)
- that all study products provided by the Sponsor were fully reconciled.

The investigator visually checked the used/unused tubes of study product returned by the subjects at study visit. In order to quantify the compliance to the treatment the Investigator also asked to the subject if the product was used according to the instructions and how many times the treatment was skipped (if any). The subject will be considered compliant to the treatment if the number of skipped applications is not exceeding 20% of the expected applications.

In the Listing 16.2.5, both accountability of returned product and adherence to treatment reported by the subject will be described.

9.1.4 Methods for Withdrawals and Missing Data

Missing data will not be replaced in any statistical analysis.

9.2 Multicenter Studies Considerations

Although two centers were planned for this investigational study, multicenter considerations will not be performed because the site 02 did not enroll any subjects.

9.3 Multiple Comparisons and Multiplicity

This was a single-arm clinical investigation and no adjustment for multiplicity will be used.

9.4 Data Safety Monitoring Board (DSMB)

No DSMB was established for this study.

10. STUDY SUBJECTS

10.1 Disposition of Subjects

Subjects' disposition by study visit will be described and summarized in the Table 14.1.1. Reasons for withdrawal will be described.

10.2 Protocol Deviations

Protocol deviations will be reviewed and discussed with the sponsor before the database lock during Data Review Meeting.

Protocol deviations will be described in the Table 14.1.2 and in the Listing 16.2.2.

11. EFFICACY ANALYSIS

11.1 Analysis datasets

The analysis of safety endpoints will be performed in the Safety population (SAF). Analysis of performance endpoints will be performed on the FAS population. The analysis of primary endpoint will be repeated in the Per-Protocol population.

11.2 Demographics and Baseline Characteristics

Demographic (gender, age, ethnic origin) and baseline characteristics will be summarized in the Tables 14.1.3 and 14.1.4 and in the Listing 16.2.4.

The descriptive statistics will include number of observations, mean, standard deviation, median, minimum and maximum for continuous variables and number of observations and their percentages for categorical parameters.

11.3 Measurements of Treatment Compliance

Treatment compliance will be assessed through the counting of the number of applications performed. The following formula will be used:

 $\frac{Number of applications performed}{Number of applications planned} * 100$

The number of planned applications will be estimated on the basis of the treatment duration x 2 times.

Treatment compliance will be estimated separately for the two study periods: Visit 1 - Visit 3 and Visit 3 - Visit 4 and it will be described in the Listing 16.2.5.

11.4 Efficacy Analysis

11.4.1 Primary Efficacy Endpoints

The primary endpoint will be the proportion of subjects with acne scars and marks improved with respect to baseline and, at the same time, without any new facial acne scars after 4 weeks of treatment (treatment success). The improvement of acne scars and marks will be assessed as the change of at least one grade in the qualitative Scar Global Assessment (SGA) by Goodman and Baron between baseline and Week 4. The number of new acne scars will be assessed by count and comparison with baseline.

The primary endpoint will be described using number (N) and the proportion of subjects (%) in the Tables 14.2.1.1 and 14.2.1.2. The proportion of treatment successes will be compared to a referent proportion (50%, Null hypothesis proportion) using the exact binomial test.

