5.1 Primary Objective and Endpoint

The primary objective of this clinical investigation is to evaluate and confirm the performance of PAPIX ACNE SCAR in the prevention and improvement of acne scars in subject suffering for mild to moderate acne, after 4 weeks of treatment.

The primary endpoint will be the proportion of subjects with improved acne scars and marks with respect to baseline and, at the same time, without any new facial acne scars after 4 weeks of treatment. The improvement of acne scars and marks will be assessed as the change in the qualitative Scar Global Assessment (SGA) by Goodman and Baron (2006) [26] between baseline and Week 4. The number of acne scars, to identify any new scars, will be assessed through the scars count and comparison with baseline.

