6.4 Procedures

6.4.1 Study Visits and Assessments

Visit 1 screening – baseline- treatment start (day 1):

Subjects will be evaluated with regard to the inclusion and exclusion criteria that will allow their participation into the study.

Before any study specific evaluation is carried out, subjects will receive all the information about the study by the Investigators and will sign an informed consent form. In the case of minors, the informed consent form shall be signed by the parents or the guardian.

The following activities will be performed:

- Collection of information about demography
- Medical and surgical history
- Acne medical history (duration, previous treatments)
- Physical examination (only dermatologic)
- Face cutaneous examination:
 - type of skin (dry/normal/oily)
 - site of acne lesions (on the face) and count
 - acne scars count
 - acne scars global assessment by the SGA
 - acne global assessment by IGA
 - roughness and skin texture evaluations
- Photographs of the face
- Previous (in the 6 months before) and concomitant medications/treatments recording
- Inclusion/exclusion criteria assessment
- Study product delivery to subject and instructions on how to use it
- Recommendations for face cleaning to follow.

Recommendations for face cleaning to follow: throughout the study subjects will be required to avoid soap and use only the product Papix cleanser for their face. The product will be provided by the Sponsor of the study. No other cleanser other than the product provided by the Investigator will be permitted.

PAPIX ACNE SCAR application: apply twice a day for 8 weeks, 2 FTU (finger tip units) in the morning and in 2 FTU the evening before bedtime, on the face, and massaged gently into the skin until absorbed.

Visits 2 and 3 – follow-up (Day 14 ± 3 and 28 ± 3, respectively):

The following activities will be done at visit 2 and 3:

- Face cutaneous examination:
 - acne scars and lesions count
 - acne scars global assessment by the SGA
 - acne global assessment by IGA
 - roughness and skin texture evaluations
- Photographs of the face
- Changes in concomitant medications/treatments recording
- Study product collection and new delivery to subject (only at visit 3)
- Treatment adherence check with the subject
- Recommendations for face cleaning to follow
- Adverse events (occurred since previous visit) recording.

Visit 4 – End of treatment and end of study (Day 56 ±3):

The following activities will be done at visit 4:

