7. SAMPLE SIZE AND STATISTICAL POWER CONSIDERATION

An exact binomial test with a nominal 5% two-sided significance level has 80% power to detect the difference between the Null hypothesis proportion, π_0 of 0.5 (i.e., 50% of subjects with treatment success) and the Alternative

proportion, π_1 , of 0.75 (i.e., 75% of subjects with treatment success) when the sample size is 30 subjects. Assuming a possible 25% dropout rate, 40 subjects were enrolled, according to the CIP provisions.

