9. GENERAL ISSUES FOR STATISTICAL ANALYSIS

9.1 Definitions, Derived Variables and Datasets

Variable	Туре	Description
lesion_num	Continous	Number of lesions
scar_num	Continous	Number of scars
srorres_iga	Discrete	Investigator's Global Assessment: 0 = Clear skin 1 = Almost clear skin 2 = Mild severity 3 = Moderate severity 4 = Severe
srorres_sga	Discrete	Scar Global Assessment: 0 = Clear skin 1 = Almost clear skin 2 = Mild severity 3 = Moderate severity 4 = Severe
srorres_rough	Discrete	Skin roughness assessment:0 = None, very smooth1 = Mild, slightly rough2 = Moderate, rough3 = Severe, very rough
srorres_texture	Discrete	Skin texture assessment: 0 = worse 1 = slightly worse 2 = no change 3 = slightly improved 4 = improved

		5 = complete improvement
qsorres_perf_subj	Discrete	Subject's global evaluation of performance: 1 = Very much improved 2 = Improved 3 = Minimally improved 4 = No change 5 = Minimally worse 6 = Worse
qsorres_perf_inv	Discrete	7 = Very much worseInvestigator's global evaluation of performance:1 = Very much improved2 = Improved3 = Minimally improved4 = No change5 = Minimally worse6 = Worse7 = Very much worse
qsorres_satisf	Discrete	Subject's overall acceptability: 1 = Very much satisfied 2 = Satisfied 3 = Neither satisfied nor dissatisfied 4 = Dissatisfied 5 = Very much dissatisfied
ecoccur	Discrete	Compliance
ecdur	Continous	Treatment skipped times
aeterm	Discrete	Adverse event description

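### The 'no new scars' half of the primary endpoint is judged from total facial scar counts, which cannot show whether any scar is new, and no use is specified for the photographs taken at every visit

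*SAP*

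**What the plan says.** SAP 11.4.1 defines treatment success at Week 4 as an SGA change of at least one grade together with the absence of any new facial acne scar. No tolerance is attached to the second condition. On how a new scar is found, the SAP says "The number of new acne scars will be assessed by count and comparison with baseline". Protocol 5.1 says the same: "The number of acne scars, to identify any new scars, will be assessed through the scars count and comparison with baseline".

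The variable list in SAP 9.1 holds one scar-count variable, scar_num, described as "Number of scars". It has no new-scar indicator, no location and no scar map. Neither document describes a recount rule, a same-assessor rule, counter training or adjudication. Protocol 7.3.5.1 refers to new lesions at the point where Protocol 5.1 and SAP 11.4.1 refer to new scars.

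Protocol 6.4.1 lists "Photographs of the face" at Visit 1, at Visits 2 and 3, and at Visit 4, and the study flow-chart agrees. Neither document gives the photographs a purpose, and the SAP has no photograph variable, reading, table or listing.

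SAP 7 states: "An exact binomial test with a nominal 5% two-sided significance level has 80% power to detect the difference" between success proportions of 0.5 and 0.75 "when the sample size is 30 subjects". Allowing for 25% dropout, 40 subjects were enrolled.

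**The concern.** The endpoint asks whether any scar at Week 4 was absent at Visit 1. That is a question about sites on the face. The data answer a different one: whether the total went up. The two can part in three ways.

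- The true total is unchanged and the Week 4 count is one too high, or the Visit 1 count one too low. A subject whose SGA improved can then be scored a failure.
- A new scar forms and the Week 4 count is one too low. The subject can be scored as having no new scar.
- A new scar forms while an old one resolves. The total is unchanged even with perfect counting.

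Counting error is plausible here. No section defines what is counted. SGA grade 1 in Protocol 6.4.2 treats flat coloured marks as scars, and all subjects enter with active acne (IGA 2 or 3), so the line between a fading lesion, a mark and a scar is left to the assessor at each visit. SGA grades severity and not number, so an improved grade with an unchanged count is a realistic pattern among responders.

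At stake is the sole primary endpoint. Overcounts pull the observed rate down towards the 50% reference. Undercounts and netting credit prevention that did not occur, which matters in an open-label single-arm study.

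**Working it through.** **1. The plan's own figure.** Inputs from SAP 7: exact binomial test, two-sided 5%, null 0.50, alternative 0.75, n = 30.

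- Rejection limit: the smallest r with P(X ≥ r | 0.50) ≤ 0.025 is 21, with upper tail 0.0214 (two-sided 0.043).
- Power: P(X ≥ 21 | n = 30, 0.75) = 0.803, so the stated 80% reproduces.
- Enrolment: 30 / (1 − 0.25) = 40. If all 40 are evaluable, the limit is 27 and power is 0.897.

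**2. How often a recount alone shows a rise.** The documents give no recount error, so this step is an assumption throughout. Let the count at each visit be the true count plus a normal error with SD s, rounded to a whole number, and let d be the true net change. A rise is recorded when d + e₂ − e₁ > 0.

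For d = 0 and independent errors, P(rise) = (1 − P(tie)) / 2, where P(tie) is the sum of squared error probabilities. At s = 0.5 the probabilities are 0.683 for error 0, 0.157 for each of ±1 and 0.001 for each of ±2. So P(tie) = 0.683² + 2 × 0.157² ≈ 0.516 and P(rise) = (1 − 0.516) / 2 = 0.242. The remaining cells follow from the same formula or by simulation.

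| Assumed error SD (scars) | No true change, independent errors | No true change, error correlation 0.8 | One scar resolved, independent errors |
|---|---|---|---|
| 0.25 | 4.4% | about 3% | 0.05% |
| 0.5 | 24% | 12% | 2.7% |
| 1 | 36% | 24% | 15% |

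The reverse error is symmetric. With one truly new scar, nothing resolved and independent errors, the comparison misses it with the first-column probabilities: 4.4%, 24% and 36%.

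**3. What lost successes would do to power.** Let q be the share of true successes scored as failures because of a false rise. With no offsetting undercounts, the observed success rate is 0.75 × (1 − q), and power is P(X ≥ 21) at n = 30 or P(X ≥ 27) at n = 40.

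| Assumed q | Observed rate | Power, n = 30 | Power, n = 40 |
|---|---|---|---|
| 0 | 75.0% | 80% | 90% |
| 2% | 73.5% | 75% | 85% |
| 5% | 71.3% | 65% | 76% |
| 10% | 67.5% | 47% | 57% |

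These q values are chosen to show sensitivity. They are not derived from the step 2 table, because the mix of unchanged and falling counts among responders is unknown.

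**4. Offsetting errors.** Suppose, as an extreme, that all of the planned 25% failures were due to new scars and 10% of them were missed, with q = 10%. The observed rate is 0.75 × 0.90 + 0.25 × 0.10 = 0.70, and power at n = 30 is 59% instead of 47%.

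**The case against.** The strongest reply is that the power loss is built on assumptions that all lean the same way. This largely stands. No recount error is documented. Independence is generous to the concern: the study is open label, one site enrolled (SAP 9.2), and nothing masks the Visit 1 count, so errors at the two visits may well be correlated. Only subjects whose SGA improved can be wrongly failed, and some of them may have fewer scars, which absorbs a one-scar overcount. The 75% in SAP 7 can also be read as the success rate as measured, with recount error already in it, in which case nothing should be deducted.

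Two stronger readings are tempting and should not be drawn. A reader might infer that the plan states a rule failing every subject whose total rises. It does not. That is the likely derivation from the variables listed, but it is not written as an algorithm. A reader might also infer that the photographs are never used. The documents specify no use, but nothing stops an investigator from consulting the Visit 1 photograph while counting.

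Nor can it be assumed that photographs would settle every case. No standard for view, lighting or resolution is given. Protocol 6.4.2 says mild scars may not be obvious at social distance, and it uses manual stretching in grading. An old scar invisible on the Visit 1 image could be called new.

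What the reply does not answer is the gap itself: a net total without location cannot establish that no scar is new, whatever the error rate.

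**Conclusion.** The measurement gap is real and can misclassify the primary endpoint in either direction. It rests on the text alone: a zero-tolerance condition, identification by count comparison, one total-count variable, and photographs with no assigned role.

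Its size is not known. The false-rise rates in step 2 depend strongly on whether any scar resolved and on how far the two counting errors are correlated. The power figures in step 3 further assume that 75% is an error-free rate and that no undercounts offset the losses. A reader might infer that the trial has lost its stated power, or that its result is biased downwards. The documents support neither, since undercounts and netting push the observed rate up.

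This is a repairable weakness that should be corrected. It does not invalidate the endpoint.

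**What to change.** **In the plan (Protocol 6.4.1 and SAP 11.4.1).** Define a new scar as one at a site not scarred at Visit 1. The investigator records it yes/no at the live examination at Weeks 2, 4 and 8, with the Visit 1 photograph as reference. The endpoint uses that field, and scar_num is reported descriptively.

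**For data already collected.** The SAP describes the study as conducted and enrolled, so a new visit field cannot help those subjects. Keep the count-based endpoint as primary and write out its derivation. Replacing it with a retrospective read by the unmasked investigator would change the primary variable after the fact and invite bias. Instead, before database lock, pre-specify a sensitivity analysis in which existing site staff compare the Visit 1 and Visit 3 photographs of every subject, not only those whose count rose, without sight of the recorded counts and SGA. Report unreadable photographs as such. The pre-lock Data Review Meeting in SAP 10.2 gives a natural deadline.

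**Cost.** One yes/no field, a few minutes per subject, and dependence on photograph quality.

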Scarring can occur as a result of damage to the skin during the healing of active acne, as scar formation is the normal and natural response of tissue to wound healing following an injury. The majority of people affected by acne scars have “atrophic scars” that are associated with a loss of collagen; a minority show “hypertrophic scars” and “keloids” [4], that are indeed characterized by more abundant collagen stretched and aligned in the same plane as the epidermis [5].

Early treatment of active acne remains the best way to prevent or limit acne-related scarring. It is also imperative to ensure active acne has been treated before approaching scar treatment so as not to create a cycle where active lesions continue to scar in areas already addressed [6]. The choice of agents used to treat acne involves the integration of multiple factors such as the severity of lesions present, duration of disease, past and present response to therapy, and tendency for scarring and post-inflammatory pigmentation. Therapy is therefore tailored to the individual patient depending on the nature and severity of their acne.

Oral antibiotics (e.g. tetracycline, minocycline, doxycycline, lymecycline) are highly effective for inflammatory acne and are widely used in clinical practice. Oral retinoids (retinol) are usually given in cases of severe acne, or for patients in whom inflammatory or pustular acne does not respond to other approaches [7].

Topical therapy is the standard of care for mild to moderate acne [8]. Many types of drugs are used, like antibiotics and retinoids, with other agents including benzoyl peroxide, salicylic acid, azelaic acid, and alpha-hydroxy acids [7]. Retinoids and antimicrobials such as benzoyl peroxide and antibiotics are the mainstay of topical acne therapy: such treatments are active at application sites, and they can prevent new lesions [9]. The main side effect is local irritation.

Gels, pledgets (medication-soaked pads), washes and solutions tend to be drying and are helpful for oily skin. Lotions, creams and ointments are beneficial for dry, easily irritated skin.

There are no general guidelines available to optimize acne scar treatment. However, there is a variety of therapies that may reduce the prominence of acne scars. The selection of an approach to treatment is based upon multiple factors such as the type and degree of acne scarring, patient preference, side effects, cost, and treatment availability [10].

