16.1 Study Discontinuation

Subjects may be discontinued at any time from the study for any of the following reasons:

- An AE occurs that, in the opinion of the Investigator, makes it unsafe for the subject to continue in the study

- Lack of compliance of the subject to the study treatment or assessments
- The subject needs to use a medication/treatment not allowed
- The subject is lost to follow-up
- The subject dies
- The subject withdraws consent
- The Investigator, for any reason, terminates the entire study, or terminates the study for that subject or the attending physician requests that the subject be withdrawn for any medical reason
- The Sponsor or the Regulatory Authority or the Ethics Committee, for any reason, terminates the entire study or terminates the study for this site or this particular subject.

If a subject is discontinued from the study, the Investigator will, as far as possible, complete the end of study visit (Visit 4) CRF pages. The Investigator should try to ascertain the reason(s) for withdrawal, while fully respecting the subject's rights.

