8. ANALYSIS POPULATIONS

8.1 Full Analysis Set (FAS)

The FAS population includes all subjects of the safety population who have performed the baseline assessments and had at least one post-baseline assessment of any performance endpoint (primary or secondary).

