8.2 Per-Protocol (PP) Population

The PP population includes all subjects of the FAS who also met all inclusion/exclusion criteria and who did not have any major protocol deviation (i.e. wrong inclusion, use of forbidden concomitant medications, etc.).

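### Starting a prohibited acne treatment before the assessed visit never in itself counts against the device, so a response reached on that treatment can be scored as a PAPIX success

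*SAP*

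**What the plan says.** **Success.** SAP 11.4.1 needs two things at Week 4: a change of at least one SGA grade from baseline, and no new facial scar by count. Neither refers to other treatment. The test follows: "The proportion of treatment successes will be compared to a referent proportion (50%, Null hypothesis proportion) using the exact binomial test". SAP 11.4.2 applies the same test to the scar endpoint at Weeks 2 and 8 and to the no-new-lesion endpoint at Weeks 2, 4 and 8.

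**Prohibited treatment.** Protocol 6.2.2 bars, among others, benzoyl peroxide, topical and oral retinoids, and topical and systemic antibiotics. It also bars scrubs, radiotherapy and unprotected sun exposure. Protocol 16.1 lists reasons for which a subject may be discontinued, one being "The subject needs to use a medication/treatment not allowed". For a discontinued subject, the Visit 4 pages are completed as far as possible.

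**Analysis sets.** The FAS (SAP 8.1) takes safety-population subjects with baseline assessments who "had at least one post-baseline assessment of any performance endpoint (primary or secondary". The per-protocol set (SAP 8.2) keeps FAS subjects who "did not have any major protocol deviation (i.e. wrong inclusion, use of forbidden concomitant medications, etc". The primary endpoint is analysed in both sets. The SAP 11.5 table gives the secondary endpoints the FAS only.

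**Missing data.** SAP 9.1.4 says that missing values are not replaced. It has no rule for withdrawals or for prohibited treatment.

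**Expected action of these drugs.** Protocol section 3 says of topical retinoids and antimicrobials: "such treatments are active at application sites, and they can prevent new lesions". It also presents early treatment of active acne as the best protection against scarring.

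**The concern.** The stated aim is to confirm the performance of the device. With one arm and a fixed 50% reference, no control group shares the effect of added treatment. A subject who adds, say, a topical retinoid in week 1 and is a responder at Visit 3 is counted exactly like a subject who responded on PAPIX alone.

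The per-protocol repeat takes the same subject out of numerator and denominator. In neither analysis does the use of another acne treatment weigh against the device. The secondary success endpoints include the no-new-lesion endpoint, on which the protocol says some of these drugs act, and they have no per-protocol repeat. At stake is whether a result just past the rejection limit can be read as device performance.

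**Working it through.** **Inputs from the documents (SAP section 7).** "An exact binomial test with a nominal 5% two-sided significance level has 80% power" with 30 subjects; null 0.50 ("i.e., 50% of subjects with treatment success"); alternative 0.75 ("i.e., 75% of subjects with treatment success"); 25% dropout; 40 enrolled.

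**Assumptions, not in the documents.** Let k be the number of evaluable subjects who start a prohibited acne-active treatment before Week 4 (starters), j the number of these who meet the success definition, and s their success probability. Shown for k = 1 to 3 and s = 0 to 100%.

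**Step 1. Reproduce the design.** With n = 30 the test rejects upward at 21 or more successes. P(X ≥ 21 | 30, 0.50) = 0.0214, so the two-sided size is 0.0428. P(X ≥ 21 | 30, 0.75) = 0.803, against the stated 80%. 30/(1 − 0.25) = 40. The plan's figures hold.

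**Step 2. Three rates from the same data.** With x observed successes among n:
- FAS as written: x/n
- Per-protocol: (x − j)/(n − k)
- Starters counted as non-success: (x − j)/n

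The FAS exceeds the third rate by j/n, which is zero when no starter responds. The per-protocol rate exceeds it whenever k > 0 and x > j, because the denominator shrinks.

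**Step 3. At the rejection limit (21/30, all starters responding, j = k).** Two-sided exact p-values against 0.50:

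| k | FAS as written | Per-protocol | Starters as non-success |
|---|---|---|---|
| 1 | 21/30 = 70.0%, p = 0.043 | 20/29 = 69.0%, p = 0.061 | 20/30 = 66.7%, p = 0.099 |
| 2 | 21/30 = 70.0%, p = 0.043 | 19/28 = 67.9%, p = 0.087 | 19/30 = 63.3%, p = 0.20 |
| 3 | 21/30 = 70.0%, p = 0.043 | 18/27 = 66.7%, p = 0.12 | 18/30 = 60.0%, p = 0.36 |

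If one starter does not respond (k = 1, j = 0), the FAS and the third rate are both 21/30, and the per-protocol rate rises to 21/29 = 72.4%, p = 0.024.

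**Step 4. Away from the limit.** 23/30 gives p = 0.005. Reclassifying two leaves 23 − 2 = 21, so 21/30, p = 0.043, which is still significant.

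**Step 5. False-positive chance.** Suppose the true rate with starters counted as non-success is exactly 50%, so that non-starters succeed at 15/(30 − k). The expected FAS rate is (15 + k·s)/30; for k = 3 this is 50%, 55% and 60% at s = 0, 50% and 100%. Upper-tail rejection probability, against 0.0214 by design:

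| k | FAS, s = 0 | FAS, s = 50% | FAS, s = 100% | Per-protocol (limit) |
|---|---|---|---|---|
| 1 | 0.0192 | 0.0326 | 0.0460 | 0.0192 (21 of 29) |
| 2 | 0.0169 | 0.0482 | 0.0913 | 0.0423 (20 of 28) |
| 3 | 0.0145 | 0.0693 | 0.1667 | 0.0383 (20 of 27) |

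If all 40 are evaluable (limit 27, design upper tail 0.0192), three starters who all respond give 0.1237.

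**Step 6. Power cost of counting starters as non-success.** P(Bin(30 − k, 0.75) ≥ 21) = 0.71 for k = 1, 0.60 for k = 2 and 0.47 for k = 3.

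**The case against.** Taking the observed outcome in the FAS whatever else was used, with a per-protocol repeat, is a recognised strategy, and the documents never adopt a rule that counts such use as failure. The upward shift is measured against a rule of the critic's choosing. The permissive wording in protocol 16.1 also heads a list that includes death and loss to follow-up, so it is weak evidence that starters stay until Visit 3. The facts are not hidden: deviations are reviewed before lock, and deviations, individual responses and concomitant medications are all listed. Evidence that these drugs shift the SGA by a grade in four weeks is thin: the protocol's statement concerns new lesions, and for retinoids on scars it cites only sparse reports.

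Much of this stands, and it rules out three stronger readings that a reader might infer:

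- *A starter is never a failure.* Not so. A starter assessed at Week 4 without a one-grade improvement, or with a new scar, is an FAS failure. What never counts as failure is the start of the treatment itself.
- *Both rates are certainly inflated.* Not so. The FAS excess is zero if no starter responds. A discontinued starter may have no Week 4 value, and the plan does not say whether that subject stays in the denominator.
- *The per-protocol repeat cannot show the problem.* Not so. In Step 3 it loses significance in every row, and its rate can lie below the FAS rate.

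What remains is that a strategy suited to a comparison of arms answers a different question here. In one arm against a fixed reference, the observed-outcome rate describes the device plus whatever was added. Listings disclose the use but do not alter the tested proportion. The per-protocol set drops these subjects and does not count them as non-successes.

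**Conclusion.** The concern holds in this limited form. Nothing in the SAP or protocol makes the start of a prohibited acne-active treatment count against the device at the assessed visit. The FAS can credit PAPIX with a response reached on such a treatment, and the per-protocol set removes the subject. Both rates can therefore exceed the rate with these subjects counted as non-successes.

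The size depends on two quantities that the documents do not give: how many subjects start such a treatment and how many of them respond. At the rejection limit, one reclassified success is enough to change the conclusion; with a margin of two successes above the limit, two reclassifications are not. The plan's sample-size figures are correct and are not in question. This should be settled before database lock, but it does not invalidate the design.

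**What to change.** Add to SAP 11.4.1 and 11.4.2, for each success/failure endpoint in the FAS:

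1. A subject who, between Visit 1 and the assessed visit, used a non-permitted treatment expected to act on facial acne or scars is a non-success at that visit, whatever the grade or count.
2. These treatments are classified at the Data Review Meeting before lock, without reference to outcome. Incidental items on the protocol 6.2.2 list do not trigger the rule: for example a single scrub, limited sun exposure, or a systemic drug given for an unrelated reason and judged not to affect the face. Applying the rule to the whole list would create failures unrelated to performance.
3. State whether FAS subjects with no value at the visit stay in the denominator.
4. Report the observed-outcome result as a supportive row.

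This is an analysis rule only and does not bear on which treatments subjects receive or when they are withdrawn. It needs no new data, because concomitant treatments are recorded at every visit. The cost is a lower success proportion if any starter responds, and less power than planned: about 0.80 to 0.71 with one starter among 30 and 0.60 with two, if non-starters succeed at 75%.
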